8. STUDY POPULATION

The precise format and content of the Study Population tables are shown in Section [12.2](#) of the RAP.

8.1. Disposition

Data displays will be produced to account for all subjects enrolled in the study. This will include the number of subjects enrolled in each population (HV or HF patients), number of subjects who have attempted or completed the DCE-MRI scan at each session, number of early withdrawals and reasons for early withdrawal. Number of subjects in each analysis population as defined in Section [5](#) will also be summarized.

The tables will use the “All subjects” population unless otherwise specified.

8.2. Demographic and Baseline Characteristics

Demography data will be summarized for safety population in this study. Disease characteristics data will also be summarized for the HF patients if data are available

These will include the following:

- Year of birth

- Gender
- Race and ethnicity
- Significant past medical history including onset, aetiology, and results of any recent relevant investigations of heart failure, as applicable
- Medication history
- Confirm heart failure class (HF patients only)
- Onset and type of symptoms (HF patients only)
- Years since diagnosis of HF (HF patients only)
- Degree of exercise intolerance-- distance/ stairs/time prior to breathlessness
- Presence of orthopnoea and/or paroxysmal nocturnal dyspnoea
- Peripheral oedema—level above ankle, non-dependent limb

9. SAFETY ANALYSES

The precise format and content of Safety figures, tables and listings are shown in Section [12.3](#) of the RAP.

The tables will use the “Safety” population unless otherwise specified.

9.1. Statistical Analyses

9.1.1. Extent of Exposure

No treatment (investigational product) will be given in this study. The number of subjects who were exposed to 1 MRI scan, 2 MRI scans, or 3 MRI scans will be summarized. Subjects who completed scan 1 and scan 2, but could not complete scan 3, with reason will be listed. If more than one patient cannot complete scan 3 due to not being able to lie down, an additional exploratory analysis will be undertaken.

9.1.2. Adverse Events

Since no investigational product will be administered in this study, information regarding the occurrence of adverse events will not be routinely collected. Medical occurrences (non-serious events) that begin during the study may be recorded under Medical History/Current Medical Conditions. Non-serious events related to study procedures may also be recorded.

Any SAEs assessed as related to study participation (e.g., protocol-mandated procedures, invasive tests, or change in existing therapy) will be recorded from the time a subject consents to participate in the study up to and including the last visit.

Any SAEs assessed as related to study procedures will be recorded. SAEs will be coded and grouped by system organ class (SOC) and preferred term using the Medical Dictionary for Regulatory Activities (MedDRA).

Based on date/time of onset, session number will be assigned to each SAE and duration from last MRI scan will be calculated.

Session	Definition
0	AEs with onset prior to Session 1 MRI
1	AEs with onset between Session 1 and Session 2 MRI
2	AEs with onset between Session 2 and Session 3 MRI
3	AEs with onset after Session 3 MRI

Frequency of SAEs will be summarized by subject population overall and by session. A SAE will only be counted once within a session.

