6.1.2. Time and Event Table for Subjects with ADHF (Group 3)

PROCEDURE	SCREENING	SESSION 1	SESSION 2 ⁴	SESSION 3 ⁵
	Following Hospital Admission For ADHF	During Hospitalization For ADHF	Up To 4 Weeks After Session 1	Up To 4 Weeks After Session 2
Informed Consent	X			
Demography/Medical History/Concomitant Medications ¹	X	X ⁸	X ⁸	X ⁸
Vital Signs including weight	X	X ²	X	X
Lung Auscultation	X	X ²	X	X
Orthopnoea Assessment	X			
Chest X-Ray ³		X ²	X	X
Oximetry	X	X	X	X
Lung Ultrasound ⁶		X ⁷	X	X
Magnetic Resonance Imaging (DCE-MRI)		X	X	X
Dyspnoea Score (5-Point Likert Scale)	X	X	X	X
Respiratory Rate	X	X	X	X
Creatinine	X	X	X	X
Haematocrit ⁹	X	X	X	X
FSH and Estradiol ¹⁰	X			
NT proBNP		X	X	X
Record Any SAEs and any AEs Related To Study Procedures		X	X	X

1. Information will be reviewed based on available hospital records
2. Assessment does not need to be repeated if Session 1 is conducted within 48 hours of Screening
3. At any designated visit, a chest X-ray need not be repeated if one has already been conducted as part of standard care
4. Session 2 will only be conducted when the pulmonary oedema is considered resolved. If pulmonary oedema is considered unresolved, only CXR and LUS may be collected.
5. Session 3 only in subjects deemed to not have pulmonary oedema resolved at session 2 by the Investigator.
6. Where feasible, Ultrasound may be performed to assess pulmonary oedema in addition to lung auscultation and / or CXR. The LUS may be completed at a separate visit (\pm 3 Days). Additional anatomic structures may be assessed during any ultrasound.
7. Multiple ultrasounds may be performed during hospitalization period of Session 1 up to one daily with a maximum of 3.
8. Sessions 1, 2 and 3 will include recording current diuretic dosage
9. Haematocrit values that are no more than 1 week old may be used
10. In women of non child bearing potential only

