6.12.1. Time Period for Collecting SAE Information

Any SAEs assessed as related to study participation (e.g., protocol-mandated procedures, invasive tests, or change in existing therapy) will be recorded from the time a subject consents to participate in the study up to and including the last visit. All SAEs will be recorded and reported to GSK within 24 hours, as indicated in [Appendix 1](#).

Investigators are not obligated to actively seek AEs or SAEs in former study participants. However, if the Investigator learns of any SAE, including a death, at any time after a subject has been discharged from the study, and he/she considers the event reasonably related to study participation, the Investigator would promptly notify GSK.

NOTE: The method of, recording, evaluating and follow-up of SAEs plus procedures for completing and transmitting SAE reports to GSK are provided in [Appendix 1](#).

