5. ANALYSIS POPULATIONS

An evaluable subject is defined as a subject that has MRI data of sufficient quality to enable DCE-MRI modelling in both Session 1 and Session 2.

All enrolled population

The all enrolled population will include all subjects who have signed the informed consent for participation in the study.

Safety population

The safety population will include all enrolled subjects who have initiated Session 1 DCE-MRI scan. All safety analyses will be based on the safety population.

For Group 3, the safety population will include all enrolled subjects who have initiated at least one session of DCE-MRI or LUS scan.

This is the population to be used for all tables, listings, and figures of patients in group 3.

Evaluable population

The evaluable population will include subjects in safety population who are 40 years and older. There is no plan to exclude subjects with major or minor protocol deviations from the analyses. However, subject data will be examined for evidence of protocol deviations in order to assess how well the protocol was followed. If necessary, any decision to exclude any subject from the planned analyses will be determined when the database is released for reporting purposes.

The evaluable populations have been changed in this RAP amendment to limit the analysis populations to subjects with age greater than 40 years old at baseline. At the interim analysis, it was realized that age may confound the results in the HV population. Since HV and HF subjects were not age-matched, limiting the analysis population to similar age range will provide a more appropriate comparison. This analysis will exclude

4 subjects; however, the study has enrolled an additional 5 subjects who are >40 years old in order to have a sufficient number of subjects for comparison. However, in addition to the comparisons using the defined populations in this RAP, a sensitivity analysis for the comparison between two groups on the change from baseline in V_e will be performed using safety population with all subjects who have evaluable MRI data in either Sessions 1 or 2.

The evaluable population definition does not apply to ADHF patients to be included in group 3 summaries.

This population is not applicable to Group 3.

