9.1.3. Deaths and Serious Adverse Events

Deaths, as well as SAEs, if any, leading to discontinuation of the study will be presented in separate listings

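### Study-related SAEs are recorded from consent, but the planned SAE summary leaves out consented subjects who were never scanned, and the promised SAE and death outputs are missing from the SAP display list

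*SAP*

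**What the plan says.** Protocol 6.12.1 sets the collection window. The events in scope are "Any SAEs assessed as related to study participation", and these "will be recorded from the time a subject consents to participate in the study up to and including the last visit". SAP 9.1.2 repeats the rule. It then assigns each SAE to a session, with Session 0 defined as "AEs with onset prior to Session 1 MRI", and plans SAE frequencies overall and by session.

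SAP 5 defines the populations. All enrolled is everyone who signed consent. For Safety, "The safety population will include all enrolled subjects who have initiated Session 1 DCE-MRI scan", and "All safety analyses will be based on the safety population". Group 3 has its own entry rule: at least one session of DCE-MRI or lung ultrasound.

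On outputs, SAP 9.1.3 states: "Deaths, as well as SAEs, if any, leading to discontinuation of the study will be presented in separate listings". SAP 10.3.6 adds that Group 3 safety, including any AEs, will be summarised. SAP 9 says where the detail is: "The precise format and content of Safety figures, tables and listings are shown in Section" 12.3.

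On scheduling, the SAE row in Protocol 6.1.1 (Groups 1 and 2) is ticked at Screening. The matching row for Group 3 in Protocol 6.1.2, "Record Any SAEs and any AEs Related To Study Procedures", is ticked only at Sessions 1, 2 and 3.

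**The concern.** The Session 0 class exists to capture events between consent and the first scan. A subject whose event in that interval prevents the scan is outside the population on which the class is tabulated, so Session 0 describes only those who went on to be scanned.

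The interval is not empty of study procedures. Protocol 3.3 places a trial of the supine position at screening and names supine dyspnoea as a key risk. Protocol 5.1 has Group 2 subjects take certain diuretics only after imaging on scan days, and Protocol 6.12.1 gives a change in existing therapy as an example of a study-related cause. Tolerability in the HF group is also one of the two grounds for stopping at the interim review (Protocol 4.1), so a serious event that keeps someone out of the scanner is relevant to a question the study asks.

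Separately, a programmer working from the SAP 12 list would produce no SAE or death output at all.

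**Working it through.** No design figure is involved, so the check compares definitions and counts displays.

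**Step 1. Collection window against analysis population.**

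| | SAE recording starts | Entry to Safety | Consented but uncounted |
|---|---|---|---|
| Groups 1 and 2 | Consent (Protocol 6.12.1); Screening is ticked and runs from 35 days to 1 day before Session 1 (Protocol 6.1.1) | Session 1 DCE-MRI initiated | Anyone who never started that scan |
| Group 3 | Consent (Protocol 6.12.1), but first tick at Session 1 (Protocol 6.1.2) | Any DCE-MRI or lung ultrasound session | Anyone with neither |

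SAP 9.1.2 names no other population for the SAE frequencies, and SAP 9 sets Safety as the default for its tables. The exclusion therefore follows from the definitions. In Group 3 the two protocol sections also disagree with each other about the interval from consent to Session 1. That interval includes the orthopnoea assessment, which Protocol 4.2.2.3 describes as a 15-minute supine test.

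**Step 2. Display count from the SAP 12 list.**

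- 12.2 (study population): 3 tables + 4 listings = 7.
- 12.3 (MRI exposure, laboratory): 4 tables + 4 listings = 8.
- 12.4 (vital signs, ECG): 4 tables + 3 listings = 7.
- Total: 7 + 8 + 7 = 22. All 22 are on Safety, none is on All enrolled, and none covers AEs, SAEs or deaths.

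SAP 12.5 adds no safety-event display. SAP 12.1 presents the list as the planned outputs for the study report. Disposition is no backstop: SAP 8.1 promises to account for all enrolled subjects, but Table 9.1 and Listing 9.2 are assigned to Safety.

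**Step 3. Size.** Let N be the number scanned, k the number consented but never scanned, x the subjects with an SAE among the scanned and e the subjects with an SAE among the never scanned. The plan reports x/N; a count matching the collection window is (x + e)/(N + k). The documents give neither k nor e, so any figure is hypothetical. Take x = 0 and e = 1:

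- HF, with the planned N = 12: 0/12 against 1/13 = 7.7% if k = 1, or 1/17 = 5.9% if k = 5.
- Group 3, with N = 3 (SAP 1, revision chronology): 0/3 against 1/4 = 25% if k = 1, or 1/6 = 16.7% if k = 3.

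If e = 0, no event is lost. These figures show only that one event would be visible in groups this small; they do not estimate a bias.

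**The case against.** Several stronger readings are tempting, and the documents do not support them.

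- *That these SAEs go unreported.* They do not. Protocol 6.12.5 requires SAEs to reach the sponsor within 24 hours, and Protocol 6.12.4 requires a death form for every death, SAE or not. SAP 7.3 says that data from withdrawn subjects will be listed, although it ties the summaries to the SAP 5 populations.
- *That no SAE or death output is planned.* SAP 9.1.2, 9.1.3 and 10.3.6 plan them. What is missing is the entry in the display list, so this is a mismatch between text and list. SAP 1 says that outputs were simplified for a small study without investigational drug, but it does not say that these were dropped.
- *That the Session 1 scan rule applies to everyone.* In Group 3 any DCE-MRI or lung ultrasound session qualifies.
- *That the lost events are mainly those caused by the imaging procedures.* Before Session 1, Groups 1 and 2 have had no study MRI, contrast or exercise test. Protocol 3.3 presents the supine trial as a precaution and expects dyspnoea to reverse quickly on sitting up. Failing it is an exclusion criterion, not in itself an SAE. Only study-related SAEs are collected from consent, so the exposed set is probably very small.

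It is also fair to say that SAP 9.1.3 names no population for its listings, so the never-scanned might appear there. That is arguable, because the general sentence in SAP 5 covers all safety analyses. The SAP 9.1.3 wording can also be read as listing only those SAEs that led to discontinuation.

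What stands after this is the exclusion from the SAE frequency summary and Session 0 row, the missing displays, and the Group 3 schedule conflict.

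**Conclusion.** The point holds as a low-severity safety-reporting correction. By definition, the planned SAE summary omits any consented subject who never started the Session 1 scan (Groups 1 and 2) or never had a DCE-MRI or ultrasound scan (Group 3). The outputs promised in the SAP text have no entry among the 22 displays in 12.2 to 12.4, and Protocol 6.1.2 conflicts with 6.12.1 on when Group 3 recording begins.

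The practical size is unknown because the documents give no count of consented but never-scanned subjects; if none of them had a study-related SAE, no event is lost. The conclusion assumes that the general sentence in SAP 5 governs the SAP 9.1.2 summary, which names no alternative. No primary or secondary endpoint is affected.

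**What to change.** 1. In SAP 5 and 9.1, state that SAEs and deaths, including Session 0, are summarised and listed on All enrolled, with never-scanned subjects shown as a separate row or column. Leave all other safety data on Safety.
2. Add to SAP 12.3 an SAE table by group and session, an SAE listing and a death listing, for Groups 1 and 2 and for Group 3. Make clear in 9.1.3 that the SAE listing covers all recorded SAEs, not only those leading to discontinuation.
3. Reconcile the SAE row of Protocol 6.1.2 with the start of collection in Protocol 6.12.1.

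The cost is some SAP wording, a few standard displays and a small protocol schedule correction. For Groups 1 and 2 no new data are needed, because recording at Screening is already scheduled. The denominator becomes larger and includes screen failures, which dilutes percentages; showing the never-scanned separately keeps the scanned denominator readable.

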3.2. Study Design Detail

For Groups 1 and 2, the study will consist of four sessions. The first visit will be a Screening Visit during which an appropriately trained study team member will describe the study, answer any questions the potential participant may have about the study seek

informed, written consent, and assess eligibility to enrol in the study. Within 35 days, subjects will return for the first scanning session, where subjects will undergo the baseline procedure. The second imaging session will occur approximately one week later to measure within-subject variability. A third imaging session (which will be conducted in 2 visits) will incorporate a bicycle exercise challenge prior to the MRI scan, and this third scan will be performed approximately one to three days after the second imaging session.

For subjects with ADHF (Group 3), Screening will occur during hospitalization to assess eligibility and enrolment in the study. Session 1 will be conducted while the subject is still hospitalized with evidence of pulmonary oedema and receiving standard of care treatment. Session 2 will be conducted within 4 weeks of the first scan, when the signs of pulmonary oedema are considered to be resolved as judged by the Investigator. If a subject's pulmonary oedema has not resolved at Session 2, as judged by the Investigator using lung auscultation and/or chest x-ray, then the subject will be not be scanned by MRI at Session 2 and will be brought back for Session 3 up to 4 weeks after Session 2 for their second MRI.

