6.1. Time and Events Tables

6.1.1. Time and Event Table for Healthy Volunteers and Subjects with HF (Groups 1 and 2)

Day:	Screening	Session 1	Session 2	Session 3 ⁴	
Visit Window	-35 to -1 days	Day 1	7±2 days after Session 1	Scan up to 3 days after Scan in Session 2	
				Visit 1	Visit 2
Informed Consent	X				
Demography/Medical History/Concomitant Medications ¹	X				
Brief Physical Examination	X	X	X	X	
Orthopnoea Assessment ²	X				
Urinalysis, Pregnancy test ³ , Drugs of abuse screen, alcohol breath test	X	X	X	X	
Electrocardiograph (ECG)	X				
Vital Signs	X	X	X	X	X
Respiratory Rate ⁶		X	X	X	X
Clinical Laboratory Assessments	X	X ²	X ²	X ²	
NT- pro BNP ²	X			X ⁵	X ⁵
Dyspnoea Scoring ⁶		X	X	X	X
Exercise Testing ⁷				X	X
Magnetic Resonance Imaging with pulse oximetry monitoring		X	X		X
DL _{CO} and DL _{NO} ⁸		X	X		X
Record any SAEs, and any AEs related to study procedures ⁹	X	X	X	X	X

1. For subjects with HF, additional history assessments are detailed in Section 6.2.
2. HF subjects only, details in the SPM.
3. Women of childbearing potential only.
4. Session 3 will be conducted over two visits. The two visits do not need to be on consecutive days.
5. In Session 3, a blood sample for NT-proBNP will be collected before and after the maximal exercise test, before the constant workload exercise test, and after the MRI scan.

6. The dyspnoea score will be obtained before and after the maximal exercise test, before the constant workload exercise test, and after the MRI scan. Respiratory rate will be measured at these same timepoints (and as indicated during the exercise testing).
7. The exercise testing (maximal exercise to exhaustion and constant workload tests) may be conducted over a two-day (consecutive or non-consecutive) period. The maximal exercise test will be conducted before the constant workload test.
8. DLco and DLno measurements will be made after each MRI scan has been completed and prior to the constant workload exercise test in Session 3 (Visit 2).
9. See Section [6.12.2](#) and Section [6.12.3](#).

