6.5. Dyspnoea Scale Scoring

After the MRI scan in Sessions 1 and 2, a standardised, validated dyspnoea 5-point Likert scale ([Mebazaa, 2010](#)) will be completed for Groups 1 and 2. In Session 3 only, the score will be completed before and after the maximal exercise test, and before and after the constant workload exercise test (before scanning) and after MRI scanning.

For Group 3, the dyspnoea 5-point Likert scale will be completed at Screening and before and after the MRI scan in Sessions 1, 2, and 3 (if needed).

Details of the scale and administration are located in [Appendix 2](#) (Section 11.2) and the SPM.

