6.10. Exercise Test

In Session 3, subjects in Groups 1 and 2 will perform two exercise tests.

Maximal Exercise Test Limited by Dyspnoea or Fatigue

Subjects will first be asked to perform a maximal exercise test limited by dyspnoea or fatigue on a cycle ergometer. Baseline measurements (heart rate, blood pressure, respiratory rate, and breath-by-breath gas exchange measurements: oxygen consumption (VO_2), ventilation/carbon dioxide production (VE/VCO_2) slope, respiratory exchange ratio (RER), and VO_2 and time at ventilator threshold) will be performed with subjects seated on the cycle ergometer for approximately 3 minutes. Subjects will then be asked to commence cycling. The workloads will be increased in a stepwise fashion until volitional fatigue. Breath-by-breath gas measurements and heart rate will be recorded throughout exercise. At the end of each workload, Borg Rating of Perceived Exertion (RPE) (See Section 11.3 [Appendix 3](#)) and blood pressure will be obtained. At peak exercise, heart rate, blood pressure, Borg RPE, and breath-by-breath gas exchange measurements including peak VO_2 will be recorded. Respiratory rate at the end of exercise will also be recorded.

Constant Workload Exercise Test

Subjects will be asked to perform cycle exercise for 10 minutes at a workload between 75% to 80% of the peak work rate achieved during the maximal exercise to exhaustion test described above. Breath-by-breath gas measurements (VO_2 , RER, exercise time) and heart rate will be measured throughout the exercise period. Blood pressure and respiratory rate will also be measured.

Full details of the exercise test protocols are included in the SPM.

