3. STUDY DESIGN

[figure not shown]
The study will enroll 12 HV and 12 HF patients. First, the DCE-MRI markers of vascular permeability and pulmonary edema will be measured in HV and HF patients at rest to determine whether there is a difference between the two populations. Next, exercise-induced changes relative to rest in interstitial volume and exchange rate will be evaluated in both HV and HF patients. Since exercise increases pulmonary vascular pressure more markedly in patients with left ventricular failure as compared to normal subjects, a greater increase in vascular permeability and pulmonary oedema may be observed in patients with HF as compared to HV.

The study consists of four visits. The first visit will be a Screening Visit during which the subjects will be assessed for their tolerance of lying flat and baseline information will be collected. Within 35 days, subjects will return for the first of two scanning sessions approximately one week apart to determine baseline levels and within subject variability. A third imaging visit will incorporate a bicycle exercise challenge prior to imaging and will occur approximately one to three days after the second imaging session.

All MRI data will be anonymized at site and transferred to Bioxydyn Limited for DCE-MRI data analysis. The 'extended Tofts' tracer kinetic model will be applied to the data to provide measurements of k^{trans} (capillary transfer coefficient of contrast agent - /min), v_e (leakage space - fraction) and v_p (plasma volume - fraction). Median values of k^{trans} and v_e will be provided from each lung (total lung, apical and basal) as well as total lung for subsequent statistical analysis. All values will be corrected for the individual's hematocrit value. If not available, a typical hematocrit value will be assumed.

In Session 3 (which will be conducted in 2 visits), subjects will perform two exercise tests. Subjects will first be asked to perform a maximal exercise test limited by dyspnoea or fatigue on a cycle ergometer. At the 2nd visit, subjects will be asked to perform cycle exercise for 10 minutes at 75%-80% of the peak work rate achieved during the maximal exercise to exhaustion test described above.

For subjects with ADHF (Group 3), the study design is shown below:

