9.1.5. Clinical Laboratory Evaluations

Haematology, clinical chemistry, urinalysis and additional parameters to be tested are listed below. Baseline clinical laboratory data will be collected for all HV and HF patients. Additional laboratory data will be collected before the MRI scan at each session for the HF patients.

Haematology

Platelet Count	Automated WBC Differential:
RBC Count	Neutrophils
WBC Count (absolute)	Lymphocytes
Hemoglobin	Monocytes
Hematocrit	Eosinophils
	Basophils

Clinical Chemistry

Urea	Potassium	Total and direct bilirubin
Creatinine	Troponin	eGFR (estimated Glomerular Filtration Rate)
Glucose	Calcium	
Sodium	AST (SGOT)	
Potassium	ALT (SGPT)	

Routine Urinalysis

Specific gravity
pH, glucose, protein, blood and ketone by dipstick
Microscopic examination (if blood or protein is abnormal)

Biomarkers**N-terminal pro-Brain-type Natriuretic Peptide (NT- pro BNP)**

*At Screening and in Session 3 only, blood samples for NT-Pro BNP determinations will be drawn before and after the maximal exercise test, before the constant workload exercise test and after MRI scanning only in subjects with HF.

Descriptive statistics and number of subjects with abnormal clinical laboratory values will be summarized by subject population and by session (in HF patients only).

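### In Groups 1 and 2, the SAP 9.1.2 session table counts an SAE that starts during or after a Session 3 exercise test, but before the Session 3 MRI, under Session 2

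*SAP*

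**What the plan says.** SAP 9.1.2 assigns every SAE a session number from its onset date and time, and in the same sentence plans to derive the time since the last MRI. Its table has four rows: 0 is before the Session 1 MRI, 1 is between the Session 1 and Session 2 MRI, 2 is "AEs with onset between Session 2 and Session 3 MRI", and 3 is after the Session 3 MRI. The numbers are then used as follows: "Frequency of SAEs will be summarized by subject population overall and by session".

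The protocol fixes the order of procedures in Groups 1 and 2.

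- Section 6.10: "In Session 3, subjects in Groups 1 and 2 will perform two exercise tests".
- Section 3.2: the third imaging session "will incorporate a bicycle exercise challenge prior to the MRI scan".
- Section 6.1.1, footnote 7: "The maximal exercise test will be conducted before the constant workload test".
- Section 6.5 has dyspnoea scored "before and after the constant workload exercise test (before scanning) and after MRI scanning", so the constant-workload test also precedes the scan. Section 6.6 gives the same order for respiratory rate.
- The time and events table in 6.1.1 shows one Session 3 MRI, at Visit 2.

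Outside 9.1.2 the SAP follows the protocol's labels. Section 3 states: "In Session 3 (which will be conducted in 2 visits), subjects will perform two exercise tests". Section 9.1.5 states: "At Screening and in Session 3 only, blood samples for NT-Pro BNP determinations will be drawn before and after the maximal exercise test". Sections 9.2.1 to 9.2.3 report vital signs, respiratory rate and dyspnoea around both tests as Session 3 data.

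**The concern.** No investigational product is given, and the SAEs described in 9.1.2 are those related to study participation or procedures. A breakdown by session is therefore useful mainly for showing which procedures the events go with. Exercise is what sets Session 3 apart from the two resting-scan sessions, and protocol 3.3 lists bicycle testing as a risk whose side effects can, rarely, be serious or threaten life.

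Under the table as written, an SAE with onset in an exercise test appears in the Session 2 row, together with anything that followed the resting scan. The Session 3 row holds only events that began after the post-exercise scan. A reader who takes the labels at face value would look for exercise events in the wrong row. The planned time since the last MRI does not solve this, because that interval does not by itself show whether exercise had started.

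**Working it through.** No power, alpha or sample-size arithmetic is involved, and the plan gives no figure to reproduce. The check applies the four rows literally to the protocol's order of procedures.

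**Order of events (Groups 1 and 2).** Session 2 MRI, then the maximal test (Session 3 Visit 1), then the constant-workload test (Visit 2), then the Session 3 MRI (Visit 2). This assumes that sessions are held in their numbered order.

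**Rule.** With M2 and M3 the times of the Session 2 and Session 3 MRI, an onset t is in row 2 if M2 ≤ t < M3 and in row 3 if t ≥ M3.

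**Illustrative times**, in hours from the Session 1 MRI, chosen inside the protocol windows (Session 2 at 7±2 days; third scan up to 3 days after the second). M2 = 7 × 24 = 168 and M3 = 168 + 72 = 240.

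| Onset | t (h) | Row under 9.1.2 | Session of the procedure (protocol; rest of SAP) |
|---|---|---|---|
| After the Session 2 scan | 169 | 2 | 2 |
| Maximal test, Visit 1 | 168 + 24 = 192 | 2 | 3 |
| Constant-workload test, Visit 2 | 168 + 71.5 = 239.5 | 2 | 3 |
| After the Session 3 scan | 168 + 73 = 241 | 3 | 3 |

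Exercise tests falling in row 2: 2 of 2. In row 3: 0 of 2. The result depends only on the order of procedures, not on the times chosen. Starting row 2 at the Session 2 visit instead of the Session 2 MRI changes nothing for exercise onsets.

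**Session 3 MRI not done.** M3 does not exist, so row 2 has no end and row 3 has no start. The onsets at 169, 192, 239.5 and 241 hours then meet no row's strict definition. SAP 9.1.1 foresees third scans that are not completed, and protocol 4.1 requires only 6 subjects per group with an evaluable post-exercise scan, against 12 per group for Sessions 1 and 2.

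**Same onsets under the proposed rows.** 169 stays in Session 2; 192 and 239.5 move to the new Session 3 row before the MRI; 241 stays in the post-MRI row. With no third scan, 192, 239.5 and 241 fall in the new row if they occur by the last visit.

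**The case against.** The strongest reply is that the SAP anchors its sessions to the scans on purpose. Section 7.5 makes the scan date Day 1 of each session, 9.1.1 counts exposure in scans, Section 5 defines the Group 1 and 2 safety population by initiation of the Session 1 scan, and 9.1.2 pairs the session number with time since the last MRI. On that view row 2 means the interval from second to third scan, and an exercise SAE is placed correctly by the printed definition. The measurements in 9.1.5 and 9.2 have nominal visits, whereas SAEs need onset windows, so some difference in convention is natural.

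This reading is plausible, and it reduces the point to labels and row boundaries. It does not remove it: the column is headed as sessions, the summary is by session, and even as an interval row 2 mixes the time after a resting scan with the exercise period.

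The reply on consequences largely stands. Each SAE gets an investigator causality assessment (protocol Appendix 1). Deaths and SAEs leading to discontinuation are listed separately (SAP 9.1.3), and third scans not completed are listed with reasons (SAP 9.1.1).

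Three stronger inferences are tempting, and the documents do not support them.

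- A reader might infer that exercise SAEs would go uncounted or that the safety conclusions are biased. The overall count by population does not use the session number.
- A reader might infer that SAEs in subjects without a third scan drop out. A programmer could leave row 2 open-ended; the SAP is silent, which is missing detail and not a rule that discards events.
- A reader might make much of the fact that none of the displays in Sections 12.3 and 12.4 is an SAE display. That too is missing detail, in a SAP whose introduction says outputs were simplified. It leaves open how the summary would be displayed.

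**Conclusion.** The point holds in a limited form. For Groups 1 and 2, the stated rule puts an SAE with onset from the start of exercise up to the Session 3 MRI under Session 2, against the protocol and the rest of the SAP. The order of procedures and the wording of the rows make this certain; whether the rows were meant as inter-scan intervals is open, and the labels would need correcting even then.

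The impact is small: one descriptive summary, possibly empty. The documents give no SAE rate, so the number of misplaced events cannot be estimated and may be zero. Overall SAE counts and every primary and secondary estimate are unaffected. Group 3 has no exercise tests and is outside the point. The case for acting is the low cost of the change and the fact that the misplaced period is that of the exercise risk named in the protocol.

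**What to change.** In SAP 9.1.2, for Groups 1 and 2:

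1. End row 2 at the start of the first Session 3 procedure, using the Visit 1 date if procedure times are not held.
2. Before the existing post-MRI row, add *Session 3, from first Session 3 procedure to Session 3 MRI (or to last visit if that MRI is not done)*.
3. Start Sessions 1 and 2 at their own first procedure as well. If only Session 3 is moved, an SAE before the scan at the Session 2 visit would still be labelled Session 1.
4. In the same edit, say that row 2 runs to the last visit if Session 3 is never started.
5. Keep the planned time since the last MRI.

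If the authors prefer scan-based windows, the alternative to items 1 to 3 is to relabel all rows as inter-scan intervals and add a separate row from the start of exercise to the Session 3 MRI.

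The cost is SAP wording and a small programming change. The documents do not say whether procedure times are in the database, hence the date fallback. One small downside is that the new row includes non-exercise time between the two Session 3 visits, which need not be on consecutive days, so it narrows the exercise period without isolating it.
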